Study Protocol with SAP

Title:

Cluster Randomized Controlled Trial: Efficacy of Gravid Oviposition Sticky Trap (GOS) and Dengue NS1 Antigen Rapid Diagnostic Test for Early Surveillance of Dengue Among Adult Aedes Mosquitoes to Reduce Dengue Outbreaks in PJU10, Damansara Damai, Selangor, Malaysia

Version date: 4 January 2019

Executive summary of study

Dengue, a serious vector-borne disease in Southeast Asian countries is fast emerging as a pandemic-prone disease globally. To add to the existing challenges, its mosquito vector, *Aedes aegypti* followed by *Aedes albopictus* are also vectors for other diseases such as chikungunya (outbreaks in 2008-2009) and Zika. In Malaysia, 120,000 cases of dengue were reported in 2015. In 2017 (until October), there were about 72,000 cases.

Surveillance are dependent on *Aedes* larval surveys and notifications of lab-confirmed human infections. However, there is no correlation between larval indices and cases of dengue. It is known that some asymptomatic people are infectious to mosquitoes. Therefore, the existing, reactive programme lacks sensitivity and is delayed, and has proven insufficient to stave off epidemics.

This current proposal unfolds a proactive and innovative paradigm shift. The creation of an in-house user-friendly technique to detect dengue virus in mosquitoes coupled with a community approach for early detection of dengue cases is an important and timely project. This proposed project will directly contribute to the Government's effort of reducing dengue as well as other vector borne diseases.

Traps will be set to collect *Aedes* mosquitoes weekly and virus will be detected in mosquitoes using dengue NS1 antigen test kit. When the positive mosquito is detected, the community will be alerted to conduct control measures (search & destroy). In the control areas, only ongoing dengue control and surveillance by the health authorities will be continued. KAP will be done before and after the intervention in intervention areas. If this study is successful, it has the potential to be a Model for Dengue Surveillance and Control and dossier to be submitted to WHO for adoption by Southeast Asian countries.

a) Research background

1. Problem Statement

Dengue is on the increase and the current surveillance and control measures are insufficient to control epidemics. The current method used is reactive rather than the proposed proactive measure.

2. Aim

This trial aims to demonstrate community effectiveness of new proactive paradigm in reducing dengue epidemics. The main hypotheses are 1) This new paradigm (GOS trap and NS1 kit) will reduce dengue epidemics compared to the usual activities carried out by the Ministry of Health (including larval control and information and education material dissemination during outbreaks) as assessed through entomology surveys. 2) Community will be more receptive to this new surveillance activity as they will receive information of infected mosquitoes before dengue cases are reported, thus will be able to take informed steps to prevent themselves from being infected.

3. Objectives

- a) To determine new paradigm (GOS trap and NS1 kit) in reducing dengue epidemics compared to the usual activities carried out by the Ministry of Health (including larval control and information and education material dissemination during outbreaks) as assessed through entomology surveys.

- b) To determine whether the community will be more receptive towards this new surveillance activity as they will receive information of infected mosquitoes before dengue cases are reported.

4. Research Questions

Will the combination of setting up traps to collect *Aedes* mosquitoes coupled with detection of virus in the mosquitoes help to reduce/prevent impending dengue epidemics? Will this method be able to cover more premises compared to house to house larval surveys? Will this method reduce the cost of dengue surveillance and control compared to the current ongoing method?

5. Literature Review

Dengue and chikungunya are major increasing public health problems across more than 150 countries (1). Dengue infection has major health impact in any person in the community including pregnant women. Study done in the University Malaya Medical Centre showed maternal dengue infection affected at least 2.5% of pregnancies in our hyperendemic setting. Vertical transmission, as defined by detection of dengue IgM in cord serum, was 1.6%. (2) Dengue infection was also found to be associated with increased risk of miscarriage. (3) In 2015, Zika virus too has become a huge public health problem in the Americas and has the potential to spread across the globe (4,5). Vector control has been the hallmark of the dengue control programme in many countries in Southeast Asia (6), since there are no anti-dengue drugs available, and the most recent dengue vaccine is partly efficacious as it falls short of the levels of protection required for a standalone intervention (7).

House to house larval surveys, source reduction, larviciding, fogging, ULV (was introduced in the 1970s and still being used) for dengue prevention and control are no longer practical and need to be augmented by more targeted but less ambitious outbreak responses that focus on a few tools that might justify expense of deployment (8). However, according to recent reports these tools are not cost effective for dengue control (9,10). Novel techniques such as the release of genetically modified mosquitoes (RIDL) and the use of the bacteria *Wolbachia* to control the population of the *Ae. aegypti* are still under trial (12-15). Urgent effective strategies for control are required ahead of the evidence from these trials, which would also require a lengthy process to assess the environmental and ecological impact of these interventions. Public and community support are important elements for these interventions to be successful.

The lack of correlation between larval indices and dengue cases (16) and the development of resistance by *Aedes* to pyrethroids and temephos insecticides (17-20) pose a serious challenge not only towards dengue control but also towards chikungunya virus and Zika virus control programmes. In many countries, studies are being conducted on the use of sticky traps to lure and trap gravid *Aedes* female adults (21-24). These traps come in different designs and some contain insecticides or incorporate pyriproxyfen to kill the progeny (25, 26). In a randomised control trial using BG sentinel traps, trapping slightly reduced the density of *Aedes* in the experimental area compared to the control area (27). However, in a trial using CDC autocidal gravid trap (AGO) there was a significant reduction between 53 to 70% in the intervention area compared to the control area (28).

In our previous phase I study conducted in an urban area in peninsular Malaysia, we showed that the infected *Ae. aegypti* mosquito was obtained from sticky non-insecticidal traps- the in-house developed sticky trap [named GOS trap (Gravid Oviposition Sticky trap)] before the first case was reported (29). This preliminary trial has shown that the sticky trap is a cheap and effective way to collect *Aedes* mosquito. Dengue virus was detected in *Ae. aegypti* before the

epidemic. The NS1 antigen test kit, a simple tool was utilised by public health staff to demonstrate the presence of infected mosquitoes and thus preventive action was initiated before an epidemic occurs. It was highlighted that a shift to this toolkit would be more efficient for a control programme than the current practice of house-to-house larval surveys. The health staff involved in this study also found that it was easier to obtain the adult mosquitoes than to carry out labour intensive larval surveys.

Subsequent to the above-mentioned phase 1 study, a prospective longitudinal phase 2 study was initiated to evaluate the use of Gravid Ovipositing Sticky (GOS) trap and the NS1 testing system for surveillance of dengue virus transmission in urban Malaysia over a two-year period. The findings showed that dengue cases would occur lag one week after infected mosquitoes are obtained and will peak at lag of 2 to 3 weeks (30). These results showed that this proactive strategy is beneficial for dengue vector surveillance programme. The usage of the GOS trap which is simple to setup, cost effective (below USD 1 per trap) and environment friendly (i.e. use recyclable plastic materials) to capture *Ae. aegypti* followed by a rapid method of detecting of dengue virus using the NS1 dengue antigen kit has shown promising results. Control measures could be initiated when positive mosquitoes are detected, for example activity such as search and destroy breeding containers. This innovative usage of GOS trap coupled with NS1 detection in mosquito provides a comprehensive early warning and surveillance system that has the predictive capability for epidemic dengue.

6. Relevance to Government Policy, if any

This cluster randomised trial is expected to provide robust estimates of the intervention effects. A rigorous evaluation of these vector control interventions is vital to the development of an evidence-based control strategy and to help direct government resources in the right direction to reduce dengue epidemics.

7. Methodology

This is a community-based study assessing the knowledge, awareness and practice on dengue infection and its prevention. We choose PJU10 because it is the dengue 'hotspot' area according to local health council. We have identified a low-cost housing area with population of approximately 48700 people.

Sample size calculation:

Sample size for intervention trial:

To test for effectiveness of intervention in reducing dengue cases, on average, each housing unit will have 2% risk of dengue per year. A sample of 5710 unit (2855 per arm) will be required to achieve 80% power at alpha of 0.05 with the assumption of reduction in 50% of risk at the end of intervention. Eight apartments with 7979 residential units will be selected and randomised into intervention and control. Apartment will be the item of randomisation.

To test for effectiveness of intervention to improve knowledge, assuming the knowledge in control group is 50% and knowledge in intervention is 70%, total sample calculated to achieve 80% power at alpha of 0.05, is 208 (104 per arm). After inflation of 20% sample required is 250 (125 per arm).

Sample size calculation for survey/cross-sectional study:

For prevalence study (knowledge), assuming baseline knowledge in population is 50%, total sample calculated to achieve 80% power at alpha of 0.05, is 384. After inflation of 20% sample required is 460.

For sero-prevalence study (blood), assuming baseline dengue sero-prevalence in population is 60%, total sample calculated to achieve 80% power at alpha of 0.05, is 369. After inflation of 20% sample required is 443.

According to the sample size calculation, the final sample size will be 500. Therefore, 250 in intervention group and 250 in the non-intervention group (control).

Phase I: KAP Questionnaire survey and blood taking

Pre-tested questionnaires will be distributed to members of community who have given consent to participate in this study.

Inclusion criteria:

- 1) All men and women aged above 18 years, including pregnant women.
- 2) Able to give consent
- 3) Willing to participate in blood taking

Exclusion criteria:

- 1) Age below 18 years
- 2) Unable to give consent
- 3) Not willing to give blood

After the questionnaire survey, 3 ml of venous blood will be taken to analyse for seroprevalence of dengue infection (dengue IgG and IgM will be carried out).

Phase II: Placement of GOS mosquito trap in the intervention group

All clusters in intervention arm will receive the GOS traps. A maximum of 21 traps will be set per apartment block, on every third floor. The traps will be monitored weekly and the abdomen of *Aedes* obtained will be tested for dengue virus using the NS1 antigen test kit. If positive search and destroy measures will be conducted by the community under the supervision of community leader and the health staff. To identify the mosquito which carries the virus, dengue NS1 antigen tests will be carried out from the head and thorax of the individual mosquitoes from positive pool of mosquitoes. For the control clusters, routine dengue control and surveillance will be carried out as per the current Ministry of Health control activity, where no traps will be set, and dengue control measure will be initiated when human cases are reported from the control group. Data collection will be conducted for 1 year and 6 months.

When a positive mosquito is obtained, flyers and banners will be distributed and hung to inform the residents of the presence of dengue transmission in the apartment block/apartment. Alternatively, the residents may also be approached house-to-house or an educational booth set up at strategic locations in the apartment to warn and educate the residents.

Phase III: Repeat of KAP questionnaire

The KAP questionnaire survey will be repeated 15 months after intervention in the intervention arm.

Phase IV: Statistical Analyses

Data of serologically confirmed dengue cases (by NS1 or IgM/IgG) from the eight residential blocks will be obtained from the Selangor State Health Department, Malaysia. It is mandatory for all hospitals and private practitioners to report cases to the Ministry of Health. The date of onset of case will be used for all data analyses.

For analysing the change in level of dengue KAP, the mean of the percentage score of the population for each domain (knowledge & attitude/practises) will be determined for the pre- and post-questionnaire. Then, paired t-test will be performed to determine the presence of significant changes in both means. A p-value of at most 0.05 indicates a significant change/improvement in the mean score (An increase in score percentage indicate a better outcome). Additionally, an individual percentage score of 80% and above indicates good knowledge/attitude/practice. Accordingly, chi-squared test will be used to determine the extent to which good knowledge is related to good attitudes/practises

All statistical analyses will be done using weekly data and R programming language for statistical analysis (version 3.2.4) (30). The family of distributed lag non-linear models (DLNM), (*DLNM* package version 2.20), which can simultaneously analyse non-linear factor-response dependencies and delayed effects, and provides an estimate of the overall effect in the presence of delayed contributions will be utilised. For dengue cases and its relation to dengue-positive *Aedes* pool, the model to be used will be: `glm(case ~ cb.total_aedes + cb.ns1positive + ns(time, 3) + woy, family = quasipoisson, data)` where `woy` = week of the year. Both the *Ae. aegypti* / *Ae. albopictus* trapped per week and cases per week at each apartment will be analysed by generalised linear mixed model (GLMM). Zero inflation and Poisson distribution were incorporated in the analysis. Differences in numbers of *Ae. aegypti* and cases between blocks and between floors were tested with Tukey's contrasts at $P = 0.05$.

References

1. Gubler, D.J., and Clark, G.G. (1995). Dengue/dengue hemorrhagic fever: the emergence of a global health problem. *Emerg Infect Dis* 1, 55.
4. Faria NR, da Silva Azevedo RS, Kraemer MU, Souza R, Cunha MS, Hill SC, et al. (2016). Zika virus in the Americas: Early epidemiological and genetic findings. *Science* 352(6283):345-9.

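### Objective (a) is to be judged by entomology surveys that have no control-arm data plan, and no intervention-versus-control analysis of dengue cases is stated

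*Combined protocol and SAP*

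**What the plan says.** **Measure.** Section 2 (Aim, hypothesis 1) and section 3 (Objectives, item a) both compare the trap-and-NS1 approach with usual Ministry of Health activity. Both end on the same measure: "information and education material dissemination during outbreaks) as assessed through entomology surveys".

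**Control clusters.** Phase II describes routine control "where no traps will be set". The Executive summary agrees: "In the control areas, only ongoing dengue control and surveillance by the health authorities will be continued". On the routine larval measure, the same summary says that "there is no correlation between larval indices and cases of dengue".

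**Sizing.** Section 7 (Sample size for intervention trial) gives its purpose as "To test for effectiveness of intervention in reducing dengue cases". It assumes that on average "each housing unit will have 2% risk of dengue per year", and that the intervention halves this. It asks for 5710 units (2855 per arm) for 80% power at alpha 0.05, and plans eight apartments with 7979 units. "Apartment will be the item of randomisation". The split between arms, and any matching or restriction, are not given.

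**Cases.** Phase IV obtains serologically confirmed cases for eight blocks from the state health department and dates them by onset. On duration, Phase II says "Data collection will be conducted for 1 year and 6 months".

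**Analyses of cases in Phase IV.** There is a distributed-lag model of cases on trap catch and NS1-positive pools. There is a GLMM of weekly mosquitoes and weekly cases at each apartment. There are Tukey contrasts between blocks and between floors.

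**The concern.** A two-arm objective needs a measure that exists in both arms and an analysis that compares them. Objective (a) names a measure for which the study plans no control-arm data. The outcome that could be available in both arms, notified dengue, is used for sizing but is not tied to the objective, not called primary and not compared by arm.

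What is at stake is prespecification of the main result. Several choices would have to be made later, possibly with case data in view: how arm enters the model, whether cases or affected units are counted, whether the period is 12 or 18 months, and how eight randomised apartments are handled. With so few clusters, such choices can decide significance.

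**Working it through.** **1. Measure against data.**

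| Data | Intervention clusters | Control clusters |
|---|---|---|
| Trap catch and NS1 in mosquitoes | Weekly | None, no traps |
| Routine larval surveys | Not stated as a study data source | May occur; no plan to obtain or compare them |
| Confirmed notified dengue | Requested | Requested, if *blocks* means the eight randomised apartments |

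Only the last row can support a comparison of arms. Its condition needs confirming, because Phase II writes of apartment blocks and apartments as if the two could differ.

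**2. Analyses against arm.**
- Lag model: its mosquito predictors exist only where traps stand. It asks how cases follow positive pools, so the absence of an arm term is no fault in it, but it does not answer objective (a).
- GLMM: it could carry an arm effect, but Phase IV lists no fixed effects, random effects or denominator.
- Tukey contrasts: their factors are block and floor, neither of which is arm. Whether they are a separate analysis or follow the GLMM makes no difference here.
- The KAP analyses (before versus after, and knowledge against practice) do not address objective (a).

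Stated arm comparisons of dengue cases: 0.

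**3. The sizing figure.** Inputs: 0.02 v 0.01, 80% power, alpha 0.05 (two-sided assumed).

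n per arm = [1.96 × √(2 × 0.015 × 0.985) + 0.8416 × √(0.02 × 0.98 + 0.01 × 0.99)]² / 0.01² = 2319 after rounding up.

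This does not reproduce 2855; with a continuity correction it is 2515. An unstated 20% allowance would come close (2319 × 1.2 = 2783; 2319 / 0.8 = 2899). At 2855 per arm, power is 87.5% if clustering is ignored. The mismatch is a separate matter. What counts here is that the calculation concerns case risk in two arms and states no allowance for clustering.

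**4. Inference with eight apartments.** The result depends on the allocation scheme, which is not stated.
- Unrestricted 4 v 4: C(8,4) = 70 allocations. The smallest two-sided permutation p for a difference in mean apartment rates is 2/70 = 0.029, and the next is 4/70 = 0.057. Only complete separation of the arms passes 0.05. A t test on apartment log rates has 8 − 2 = 6 df (critical value 2.447).
- Four matched pairs: 2⁴ = 16 allocations, smallest two-sided p 2/16 = 0.125, so a permutation test can never reach 0.05. A paired t test has 4 − 1 = 3 df.

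**5. Why the 80% does not carry over.** For illustration, assume unrestricted 4 v 4, m = 7979/8 ≈ 997 units per apartment, 12 months, 2% v 1%, a t test on apartment rates with 6 df, and a between-apartment coefficient of variation k. The documents give no k.

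SE = √{[(0.0196 + 0.0099)/m + k²(0.02² + 0.01²)]/4}; noncentrality = 0.01/SE.

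| k | 0.01/SE | Power |
|---|---|---|
| 0 | 3.68 | 86% |
| 0.1 | 3.40 | 81% |
| 0.25 | 2.56 | 57% |
| 0.5 | 1.61 | 27% |

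**The case against.** Much is already fixed. The sample-size section sets dengue risk per unit as the sizing outcome. Phase IV sets the case definition, source and date variable, and commits to a GLMM of weekly cases at each apartment, which is the randomised unit. One may fairly say that arm is implied in that model. This stands as far as it goes and narrows the gap. But an implied effect is not a stated one, and the denominator, period, counting unit and inference method are still open.

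The entomology clause directly follows the description of usual Ministry activity and could be read as describing that activity. This reading is possible but less natural. It does not remove the problem either, since objective (a) would then name no measure at all.

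Routine larval surveys may exist in control areas. No section plans to obtain them, and the Executive summary itself denies that larval indices track cases.

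Finally, the choice of primary outcome and test belongs to the investigators. That is right. The point is that both be stated, and dengue cases are the choice consistent with the plan's own sizing.

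**Conclusion.** The point holds. As written, the measure named for objective (a) cannot give a between-arm answer, because no control-arm entomological data are planned, and Phase IV states no intervention-versus-control comparison of the outcome the trial is sized on. This is more than missing detail and should be settled before analysis.

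Two stronger readings go too far. A reader might infer that even the sizing outcome would be chosen after the data are seen; the sample-size section already fixes it. A reader might also infer that the trial cannot compare the arms at all; the planned case data would allow it, provided that *blocks* means the eight randomised apartments.

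The conclusion itself rests on the text and not on any number. The permutation p-values and degrees of freedom in the working hold only for the allocation named beside each. The power figures rest on an assumed k.

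**What to change.** 1. In hypothesis 1 and objective (a), replace the entomology clause with serologically confirmed notified dengue, by date of onset, in all eight randomised apartments, and name it the primary outcome. Confirm that *blocks* in Phase IV means those apartments. State the counting period (sizing uses a yearly risk; collection lasts 18 months) and whether cases or affected units are counted. Counting affected units matches the sizing but needs unit-level addresses, which Phase IV does not say will be supplied.
2. In Phase IV, add one prespecified between-arm comparison with arm as the effect, residential units as the denominator and the apartment as the unit of inference. Use a small-sample method matched to the allocation actually used, and state that allocation. If it was unrestricted 4 v 4, a t test on apartment log rates is one option; it relies on approximate normality. If the apartments were matched in pairs, the analysis must respect the pairs.
3. Label trap catch, NS1 positivity and the lag model as intervention-arm surveillance measures with no between-arm claim.

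The cost is wording, one clarification and one analysis, using data already requested. If *blocks* turns out to mean something else, the data request must be widened. The trial gives up a between-arm entomological claim for which it has no data plan. The 80% power must be recalculated, with clustering, before it is quoted for this analysis.

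### The stated 2,855 units per arm and 80% power do not describe the planned trial: the 2% annual risk is not reconciled with 18 months of data collection, and no between-apartment variance is included.

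*Combined protocol and SAP*

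**What the plan says.** All of the following is in section 7, Methodology.

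- **Sample size for intervention trial.** The baseline is that "on average, each housing unit will have 2% risk of dengue per year". The sample is 5,710 units, 2,855 per arm, which "will be required to achieve 80% power at alpha of 0.05", "with the assumption of reduction in 50% of risk at the end of intervention". The text gives no sidedness, no period over which the risk accumulates, no allowance for losses, and no ICC or design effect.
- **Same paragraph, on design.** "Eight apartments with 7979 residential units will be selected and randomised into intervention and control". "Apartment will be the item of randomisation".
- **Phase II.** "Data collection will be conducted for 1 year and 6 months". No separate length is given for the intervention.
- **Phase III.** "The KAP questionnaire survey will be repeated 15 months after intervention in the intervention arm". This is the only other statement on timing.
- **Phase IV.** Weekly cases per apartment are to be analysed by a generalised linear mixed model. No 12-month limit on cases is mentioned.

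**The concern.** A comparison of two proportions needs the risk over a defined follow-up. The only risk given is annual, the only collection period given is 18 months, and the effect is placed at the end of an intervention of unstated length. If all 18 months of cases count, the expected number of cases per arm is about half as large again as the calculation assumes.

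At stake is whether the stated size, power and detectable effect can be relied on. The period also feeds the cluster calculation that the plan still lacks. If a design effect were simply added to the present figure, the unresolved period would carry over into the new one.

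**Working it through.** **Inputs.** From the plan: control risk 2% per year, 50% reduction, 80% power, alpha 0.05, 2,855 units per arm, eight apartments, 7,979 units, 18 months. Assumed here: two-sided test, four apartments per arm, even split of units, and the ICC or coefficient of variation, for which the plan gives no value.

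**1. The plan's own figure.** The pooled two-proportion formula is

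n = [1.960 √(2p̄(1−p̄)) + 0.842 √(p₁(1−p₁) + p₂(1−p₂))]² / (p₁−p₂)².

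For 2% v 1%: (0.3369 + 0.1446)² / 0.01² = 2,319 per arm, or 2,515 with continuity correction. A one-sided test gives 1,826, unpooled variance 2,316, arcsine 2,254, Poisson rates 2,355, and Fisher's exact test about 2,450. None gives 2,855.

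The figure is approached only by adding something the plan does not state. The 20% allowance used elsewhere in the section gives 2,319 × 1.2 = 2,783 or 2,319 / 0.8 = 2,899. A continuity correction with a 12% allowance (2,515 / 0.88 = 2,858), or one with 85% power (2,849), also comes near. None of these is documented for this calculation.

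**2. The 18-month risks.** Simple scaling gives 3% v 1.5%: (0.4111 + 0.1763)² / 0.015² = 1,534 per arm. Compounding gives 1 − 0.98^1.5 = 2.985% v 1 − 0.99^1.5 = 1.496%, which needs 1,551. Even with a 20% allowance (1,551 × 1.2 = 1,862), this does not reach 2,855.

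**3. What 2,855 per arm delivers without clustering.** Power = Φ{[√n (p₁−p₂) − 1.960 √(2p̄(1−p̄))] / √(p₁(1−p₁) + p₂(1−p₂))}.

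- 2% v 1%: (0.5343 − 0.3369) / 0.1718 = 1.149, so power is 87.5%.
- 3% v 1.5%: (0.8015 − 0.4111) / 0.2095 = 1.864, so power is 96.9% (96.7% with the compounded risks).
- Smallest reduction detectable at 80% power: about 46% on the one-year risk and 38% on the 18-month risk.

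**4. Adding the apartments.** Design effect = 1 + (m − 1) × ICC, where m is the number of units per apartment: 2,855 / 4 = 713.75 for the stated size, and 7,979 / 8 = 997.4 for all selected units (about 3,989 per arm). Power is recomputed at n divided by the design effect, with the compounded 18-month risks.

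| Assumed ICC | Design effect, 2,855 per arm | Power, one-year risks | Power, 18-month risks | Power with all 7,979 units, one-year / 18-month |
|---|---|---|---|---|
| 0 | 1.00 | 87.5% | 96.7% | 96% / 99% |
| 0.001 | 1.71 | 66% | 83% | 74% / 89% |
| 0.002 | 2.43 | 51% | 68% | 57% / 74% |
| 0.005 | 4.56 | 31% | 43% | 32% / 45% |
| 0.01 | 8.13 | 19% | 27% | 20% / 27% |

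These use a normal approximation, which is optimistic with eight clusters. At 2,855 per arm, 80% power is lost once the ICC exceeds about 0.0003 on one-year risks or 0.0012 on 18-month risks.

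**5. A check that does not hold the ICC fixed.** If apartment rates vary in proportion to their mean, with coefficient of variation k, the number of apartments per arm is

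c = 1 + (1.960 + 0.842)² [(λ₀+λ₁)/y + k²(λ₀²+λ₁²)] / (λ₀−λ₁)²,

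with λ₀ = 0.02, λ₁ = 0.01, and y = 997.4 unit-years per apartment over one year or 1,496.1 over 18 months. At k = 0.1, c is 3.8 or 3.0; at k = 0.25, 5.8 or 5.0; at k = 0.5, 13.2 or 12.4. The longer period saves about 0.8 of an apartment per arm whatever the value of k.

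**The case against.** Four things can be said for the plan.

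1. **The plan does not define an 18-month endpoint.** A reader might infer one, but the text says only that the effect is at the end of the intervention, and the 18 months describe data collection. This stands. What the documents support is a period left unstated and unreconciled.

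2. **The annual figure may be meant as a rate, with 50% as a rate ratio.** The planned weekly-count model fits that reading, and an annual input is then legitimate. This stands in part, because sizing by rates still needs the unit-time of follow-up, and none is shown.

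3. **The mismatch errs on the safe side.** This stands in full. A longer period lowers the required size by about a third (2,319 to between 1,534 and 1,551) and raises power. A reader might infer that the annual input leaves the trial too small, but the arithmetic shows the opposite.

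4. **The missing between-apartment variance is the larger defect, and correcting it would force the period to be stated.** This also stands, and is why both belong in one recalculation. The period still matters: at an assumed ICC of 0.001, it alone decides whether 2,855 per arm falls short of 80% (66%) or exceeds it (83%).

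The opposite inference, that 18 months of cases leaves ample reserve for clustering, is not supported either. Longer follow-up does not remove variation between apartments. If that variation is proportional to risk, four apartments per arm are too few at k = 0.25 on either period.

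**Conclusion.** The point holds: 2,855 units per arm at 80% power matches neither a one-year nor an 18-month comparison, and takes no account of the eight apartments. Without clustering, the stated size would give about 87.5% or 97% power, and could detect a reduction of about 46% or 38%. Part of that departure from 80% and 50% arises because 2,855 does not follow from the stated inputs even for one year. The period accounts only for the step from 87.5% to 97% and from 46% to 38%.

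With clustering, power could lie anywhere from comfortable to very low. The documents give no ICC, so they do not show that the trial is underpowered. They show that the stated power has no basis under the planned randomisation. The results rest on a two-sided test, four apartments per arm with an even split, constant risk over time, and the assumed ranges of ICC and k.

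**What to change.** In the sample-size section:

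1. State the follow-up period of the primary case comparison. If 12 months is intended, limit the primary case count to 12 months.
2. Recalculate with the rate over that period. If all 18 months count, that is 2% per unit-year times 1.5 years, about 3% v 1.5%.
3. Include a between-apartment ICC or coefficient of variation over a stated range, using a method suited to eight apartments.
4. State the sidedness of the test and any inflation applied, so that the figure can be reproduced.
5. Restate power and the smallest detectable reduction for the 7,979 units selected.

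The cost is one recalculation and a revised paragraph. The recalculation itself changes nothing in recruitment, trapping or case collection. If it shows low power over the plausible range, the plan should say so.
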